1.4. Sample Size Justification

The primary effectiveness endpoint is the change from baseline in the KCCQ-TSS at the end of the 12-week double-blind treatment period. Although a 5-point improvement in the KCCQ-TSS is generally viewed as clinically meaningful,^{2,12} recent studies^{7,8} have shown that improvements in the range of 3 to 5 points on the KCCQ-TSS are equally meaningful in the overall HF-related health status measured by the KCCQ over a 12-week time period. In considering the clinical significance of scores, it is important to separate mean changes for groups of participants, as compared with intra-individual changes. On the TSS, there are 7 items (4 for symptom frequency and 3 for severity/burden).^{3,11} Shifting a response on KCCQ questions 5 and 7 shifts the TSS score by 2.083 points on a 100-point scale. A shift in response for questions 3 and 9 shifts the score by 3.125 points and for items 4, 6, and 8, shifts the score by 4.166 points, assuming no missing responses. Thus, an intra-individual change of at least 2 categories (3 if the only change is in items 5 and 7) would exceed the 5-point threshold that has been shown to be clinically significant. When analyzing groups of participants, the mean difference across the entire population includes a distribution of participants with different magnitudes of individual change and a 3- to 5-point difference between groups reflects a significantly larger proportion of participants in one group, as compared with the other, who have clinically important improvements in their TSS.

Thus, based on the totality of evidence evaluating the clinical significance of the KCCQ,^{5,6,9,14} a between group difference of 3 points is considered clinically meaningful and the current study is powered to detect a mean change from baseline of 3 points in the KCCQ-TSS between canagliflozin 100 mg and placebo groups at Week 12. Assuming a significance level of 5% and a

standard deviation (SD) of 18 points for mean change in KCCQ-TSS, a total of 1,900 participants will be randomized in this study providing approximately 95% power. This sample size is adequate to account for a potential 5% to 10% dropout rate - that is, with a dropout as high as 10% [$n=1,710$], the statistical power remains $>90\%$.

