The mean differences between the groups will be augmented with both responder analyses and empirical cumulative distribution and probability density function curves. Specifically, the empirical cumulative distribution function (CDF) of the change from baseline in KCCQ-TSS will be generated. CDF shows the proportion of the population scoring less than or equal to each possible change score. CDFs are useful as they graphically characterize the treatment effect or differences between groups. It also enables a ready assessment of different magnitudes of clinical change (e.g., 5, 10, and ≥ 20 -point changes, corresponding with small to moderate, moderate to large, and large to very large clinical changes). CDFs and histograms will be shown for changes from baseline to Week 12 in the KCCQ TSS. For all CDF plots, the x-axis is the score change from baseline to final time point (i.e., Week 12) for the KCCQ-TSS. The y-axis is the cumulative proportion of the participants in each of the corresponding categories that reach the score change on the x-axis.

According to the Food and Drug Administration's (FDA's) guidance on PRO measures, a responder is defined by the empirically determined score change in a measure, experienced by an individual patient over a predetermined time period that has been demonstrated in the target

population to have a significant treatment benefit. This is also often referred to as responsiveness or ability of the PRO measure to capture the true underlying change in the patient health status over time. Assessing the responsiveness of the PRO measure using an anchor-based approach involves comparing the changes in the PRO scores to other clinically meaningful markers or anchors that represent a valid measure of clinical change.

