For the anchor-based analysis of the KCCQ-TSS endpoint, participants will be characterized based on the PGIC scores at Week 12. The mean change in KCCQ-TSS endpoint observed in the smallest improvement category of the PGIC will be examined as a key anchor-based indicator of a responder. The definition for a small improvement in PGIC is given as those who improve by one category (i.e., from “a little improved” to “somewhat improved”). Specifically, the retrospective PGIC responses of “3=a little improved” will be selected to represent time points where participants register meaningful changes in their HF symptoms. Each time a participant responds with a PGIC score of “3=a little improved”, a KCCQ-TSS change score from the preceding visit is computed. For the double-blind treatment period, the PGIC will be collected at 4 time points (i.e., Weeks 2, 4, 6, and 12 respectively) which can yield between zero and 4 KCCQ-TSS change scores by each participant. For each participant with at least one PGIC response of “3=a little improved”, a mean of the individual participant’s KCCQ-TSS change scores is computed. A summary of KCCQ-TSS change scores across PGIC categories¹⁶ will then be presented.

The KCCQ-TSS change scores may also be standardized into effect size (ES) statistics by dividing them by their SD at baseline. The following cutoff values will be used to interpret effect size: small ES = 0.2, moderate ES = 0.5, and large ES = 0.8. Together with the CDF, results from the anchor-based methods will be examined and a single responder definition threshold will be determined, if the results from the anchor-based assessments in this study differ substantially from prior studies examining the clinical meaningfulness of changes in the KCCQ.

In addition, a distribution-based change (i.e., minimum detectable [MID] change) may be explored for which the KCCQ-TSS can be derived using the baseline SD. Generally, a value of half the baseline SD has been frequently found to correspond to the MID obtained via the anchor-based method. A value of $0.2 \times \text{SD}$ may also be examined.

Subgroup analyses for the change from baseline to Week 12 for the primary effectiveness endpoint will be conducted for subgroups (listed in Section 2.4) based on all randomized analysis set. These analyses will assess consistency of the overall treatment effect across subgroup variables.

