5.4.2. Analysis Methods

The exploratory endpoints listed below will be presented using descriptive statistics at each time point measurements are taken. Where specified, 95% confidence intervals (CIs) and p-values will be presented but no multiplicity adjustment will be made. Analyses of mean changes from baseline to Week 12 and month 9 (Day 252) respectively will be conducted, as described below.

- Appendix 6: Patient Global Impression of Change (PGIC) is a validated generic tool for assessment of overall change in the severity of illness following treatment. Participants rate how they feel now compared with how they felt before receiving study intervention on a 7-point scale where 1 is “Very much improved” and 7 is “Very much worse”. A mean \pm SD PGIC score for each time point will be calculated by randomized intervention group. Distribution of PGIC score at Week 12 will also be presented. Based on the PGIC symmetric scale, a dichotomous scale of “Yes” or “No” will be derived. A favorable change is score of 1-3 = ‘Yes’, which means there is significant improvement with the study intervention. If the response is 4-7 = ‘No’, it is considered no significant change. Change in the KCCQ-TSS from baseline to Week 12 by PGIC response at Week 12 will be summarized by treatment group, and, also graphically displayed (i.e., x-axis will display categories of PGIC response at Week 12 and y-axis will display mean change scores from baseline to Week 12 in KCCQ-TSS by treatment group).
- Distribution of participants in PGI-S (see [Appendix 7: Patient Global Impression of Severity \(PGI-S\)](#)) response categories will be summarized by randomized intervention group at baseline and by Week 12. Mean change in PGI-S score between baseline and Week 12 will be summarized by randomized group. Change in the KCCQ-TSS from baseline to Week 12 by PGI-S response at Week 12 will be summarized.

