Appendix 6: Patient Global Impression of Change (PGIC)

Appendix 6 provides a representative example of the scale questions that will be used in this study.

Since the start of the treatment you've received in this study, your heart failure symptoms are: (select one response)

1. Very much improved
2. Somewhat improved
3. A little improved
4. No change
5. A little worse
6. Somewhat worse
7. Very much worse

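### The anchor rule in SAP 5.2.3 pairs a since-start-of-treatment PGIC rating with KCCQ-TSS change since the previous visit, so the two periods match only at Week 2

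*SAP*

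**What the plan says.** The anchor paragraph of SAP 5.2.3 opens by saying that "participants will be characterized based on the PGIC scores at Week 12", and treats the mean KCCQ-TSS change in the smallest PGIC improvement category as a key indicator of response. It then gives two further instructions.

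- **Definition of small improvement.** "The definition for a small improvement in PGIC is given as those who improve by one category", illustrated by a move from 'a little improved' to 'somewhat improved'.
- **Working rule.** PGIC = 3 ('a little improved') is selected at any of Weeks 2, 4, 6 and 12. Each time it occurs, "a KCCQ-TSS change score from the preceding visit is computed". A participant can supply zero to four such changes, and these are averaged within participant.

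The PGIC item in SAP Appendix 6 begins "Since the start of the treatment". Protocol 8.2.1 has the same wording, and SAP 5.4.2 describes the item as comparing now with the time before study intervention.

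On use, SAP 5.2.3 says the anchor results are read with the cumulative distribution function, for which "the x-axis is the score change from baseline to final time point" (Week 12), and that "a single responder definition threshold will be determined, if the results from the anchor-based assessments in this study differ substantially from prior studies".

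SAP 5.4.2 separately plans a matched summary: "Change in the KCCQ-TSS from baseline to Week 12 by PGIC response at Week 12 will be summarized by treatment group". Protocol 9.4.2.2 plans the corresponding association at Month 3.

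**The concern.** An anchor analysis is informative only if the anchor and the score change describe the same period. Here the rating looks back to the start of treatment, while the score change looks back one visit. Improvement achieved before the preceding visit counts in the rating but not in the score.

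If participants who rate themselves a little improved were, on average, already above baseline at the preceding visit, the rule understates the change that goes with that rating. That is the natural expectation in a trial of symptom improvement, but it is not certain.

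The paragraph is also inconsistent with itself. It opens with Week 12 PGIC, works with all four visits, and defines small improvement as a step between two PGIC categories before selecting one category. Two programmers could produce different numbers from it.

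What is at stake is the interpretation of response. A low anchor value could be taken as differing substantially from prior work, which is the SAP's condition for setting a new threshold. That threshold would then be applied to change from baseline to Week 12, a scale on which the anchor value was not measured.

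**Working it through.** **Inputs.** KCCQ-TSS is measured at baseline and Weeks 2, 4, 6 and 12 (SAP 5.2.3). Baseline is the last observation before first dose (SAP 2.6), so it is the visit preceding Week 2. The PGIC period is from SAP Appendix 6 and the pairing rule from SAP 5.2.3.

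**The SAP's own count.** Five KCCQ occasions give four preceding-visit intervals, so zero to four changes per participant. This reproduces the SAP's figure.

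**Periods compared**, assuming no missed questionnaire:

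| PGIC visit | PGIC covers (weeks) | Score change covers (weeks) | Share of PGIC period |
|---|---|---|---|
| Week 2 | 0–2 | 0–2 | all |
| Week 4 | 0–4 | 2–4 | 1/2 |
| Week 6 | 0–6 | 4–6 | 1/3 |
| Week 12 | 0–12 | 6–12 | 1/2 |

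The periods match at one visit of four.

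**Size, in general.** Let C(t) be the change from baseline at visit t, with C = 0 at baseline, and let t−1 denote the preceding visit.

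- The rule gives C(t) − C(t−1).
- The matched value is C(t).
- Rule minus matched = −C(t−1), for any trajectory.

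**PGIC = 3 at all four visits, complete data.** The four differences sum to C(12), so the participant's mean is C(12)/4. With C(12) = 5 this is 5/4 = 1.25, whatever the path. The shortfall depends on the comparator:

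- Against the Week 12 change, the rule always gives one quarter (1.25 v 5).
- Against the mean of the four same-visit changes from baseline, it depends on the path:
  - immediate plateau (5, 5, 5, 5): mean 5, so one quarter;
  - linear (0.83, 1.67, 2.5, 5): mean 10/4 = 2.5, so one half;
  - all gain after Week 6 (0, 0, 0, 5): mean 1.25, so no difference.

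For scale, SAP 1.4 states: "Shifting a response on KCCQ questions 5 and 7 shifts the TSS score by 2.083 points on a 100-point scale". This is the smallest one-category shift, and it checks against the scoring in SAP Appendix 8: 100/4/6/2 = 2.083. The other items give 100/4/4/2 = 3.125 and 100/3/4/2 = 4.167.

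**PGIC = 3 at Week 12 only, 5-point gain at Week 12.** The matched value is 5 on every path. The paths are assumed.

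| Path at Weeks 2, 4, 6, 12 | Rule: C(12) − C(6) |
|---|---|
| 5, 5, 5, 5 | 5 − 5 = 0 |
| 0.83, 1.67, 2.5, 5 | 5 − 2.5 = 2.5 |
| 0, 0, 0, 5 | 5 − 0 = 5.0 |
| −4, −4, −2, 5 | 5 − (−2) = 7.0 |

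**Group level, assumed inputs only.** A simulation of 200,000 participants used six mean trajectories with person SD 0, 6 or 12, visit noise SD 7 and measurement error SD 8. PGIC was set to 3 when true change plus rating noise (SD 4) lay between 4 and 10. Rule minus same-visit matched value ran from −4.9 (early plateau, 2.01 v 6.91) to +4.0 (early worsening then recovery, 8.79 v 4.77). Both size and direction depend on the trajectory.

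**The case against.** The strongest reply is that the SAP already names the right analysis. Its opening refers to Week 12 PGIC and to the KCCQ-TSS endpoint, which SAP 5.2.1 defines as baseline to Week 12, and SAP 5.4.2 plans exactly that pairing. On this reading the later sentences are a drafting slip. The reading is possible, but the sentences that spell out the calculation say otherwise, and a programmer would follow them. SAP 5.2.3 does not point to the 5.4.2 summary as the basis for a threshold.

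Four further points stand and limit the conclusion.

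- Neither the direction nor the size of the error is established. The documents give no trajectory, and the paths and simulation inputs above are assumptions.
- The one-quarter result holds on every path only against the Week 12 change. Part of that gap comes from pooling earlier visits and would remain if same-visit changes were pooled. The 2.083 figure is a one-person yardstick, whereas a threshold would come from a group mean.
- Harm needs several steps: a low value, a judgement that it differs from prior studies, and too little weight given to the distribution curves, the 5.4.2 summary and any distribution-based check.
- The match at Week 2 only assumes complete questionnaires. If 'preceding visit' means the last available score, a participant who missed every earlier post-baseline KCCQ would also match later. The SAP does not say which is meant.

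None of this makes the preceding-visit pairing suitable for a rating made since the start of treatment.

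**Conclusion.** The concern holds: the working rule is wrong as written, not merely short of detail. On the scheduled visits it matches the PGIC period at Week 2 only. Its error relative to same-visit change from baseline is exactly minus the change reached at the preceding visit. It is therefore too low when participants giving the rating had, on average, already improved by then, nil when they had not changed, and too high when they had worsened. The mismatch is certain from the text; a too-small threshold is a plausible consequence, not a demonstrated one.

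The reach is limited to the exploratory responder interpretation. The primary MMRM, type I error control, the sample size, the 3-point between-group difference and the pre-set 5- and 10-point responder analyses do not depend on this anchor. It should be corrected because the remedy is simple and the result may set a threshold.

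**What to change.** In SAP 5.2.3:

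1. Replace change from the preceding visit with KCCQ-TSS change from baseline to the same visit as the PGIC response. The periods then match at all four visits (0–2, 0–4, 0–6 and 0–12 weeks), and missed questionnaires no longer alter the period.
2. State that Week 12 PGIC with baseline-to-Week 12 change, the summary already planned in SAP 5.4.2, is the analysis that informs any threshold. Weeks 2, 4 and 6 are supportive and are not pooled into it.
3. Define the anchor group as PGIC = 3, read beside PGIC = 4 ('no change'). The planned displays across PGIC categories already include both.
4. Delete the definition based on moving from 'a little improved' to 'somewhat improved'.

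The cost is a few sentences. No new data are needed, and the governing summary is already planned.

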5.3. Secondary Endpoints

5.3.1. Definition

The first key secondary effectiveness endpoint is change in the daily step count from baseline to Week 12 averaged over two-week intervals. Even though evidence of a meaningful change in daily step count in chronic HF patients via Fitbit device is not readily available, there are several studies that have conducted six-minute walk tests (6MWT) among HF patients in general and examined a minimum clinically important difference in daily step counts under different conditions. A change of 30 meters¹⁰ (approximately 1000 steps) may be considered in the present study to be of clinical interest to benchmark the expected mean change in daily step count in this study over the double-blind treatment period. This expected mean change in daily step count will also be examined in relation to variables such as PRO measures (as anchors) and clinical outcomes to better characterize treatment effect on daily activity.

As HF patients are generally not consistent in their daily walk patterns, there will be variations in levels of their daily activity (whether it is a weekday or a weekend) as well as variability in the total wear time of the Fitbit device. As a rule, we will consider Fitbit recorded ≥ 100 steps¹³ taken in a day in the calculations of averages. This will ensure capturing any meaningful level of physical activity while avoiding even smaller variations in daily steps taken by a participant wearing a Fitbit device. For each participant, baseline daily step count will be calculated by averaging daily step counts from Study Day 1 through Study Day 14. All subsequent post-baseline daily step count data will also be averaged in 2-week intervals. The change from baseline to Week 12 in daily step count will be based on subtracting the average of daily step count for Week 11 and Week 12 from the baseline average for each participant. Additionally, daily step count data will be averaged in 3-, 5- and 7-day (1-week) intervals at baseline and throughout the treatment period respectively and corresponding changes from baseline will be calculated.

The variable daily floors climbed will also be aggregated in a similar fashion.

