1.1. Objectives

Primary Objective

The primary objective is to determine the superiority of the effectiveness of canagliflozin 100 mg daily versus placebo in participants with symptomatic HF in improving the overall KCCQ-TSS.

Secondary Objectives

The first key secondary objective is:

- to determine the superiority of the effectiveness of canagliflozin 100 mg daily versus placebo in improving the total daily step count.

The second key secondary objective is:

- to determine the superiority of the effectiveness of canagliflozin 100 mg daily versus placebo in improving the KCCQ individual domain scores (physical limitation, quality of life, clinical summary, and overall).

Exploratory Objectives

The exploratory objectives are to assess the effectiveness of canagliflozin 100 mg daily versus placebo in participants with symptomatic HF by:

- responses on the Patient Global Impression of Change (PGIC) and the Patient Global Impression of Severity (PGI-S)
- healthcare resource utilization (HRU) and health economics data
- associations (correlations and/or categorical association measures) between digital markers (step count and floors climbed), and clinical events such as need for outpatient intravenous therapies, emergency department (ED) visits, and hospitalizations
- daily floors climbed
- time to first hospitalization/readmission for HF
- time to first hospitalization/readmission for other events
- time to death
- the participant's satisfaction with their experience with the virtual design at the end of the study (see [Appendix 2: Participant Satisfaction Survey](#)).

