5.3.2. Estimand

The first key secondary estimand to be estimated in the study, is defined by the following -

- Population: FAS (i.e., all randomized participants with HF who either have HF_rEF or HF_pEF, regardless of T2DM status with at least one dose of study intervention and at least 1 post-baseline KCCQ measurement)
- Treatment: canagliflozin 100 mg or placebo

- Variable: change from baseline to Week 12 in the daily step count averaged over 2-week intervals
- Intercurrent event: treatment discontinuations (either due to AE or other reasons) or treatment switching or temporary disruption in daily activity; use treatment policy strategy to address intercurrent events (i.e., use all available measurements collected during study, regardless of the occurrence of the intercurrent event); events of “loss to follow up” or “study withdrawal” or “death” are not considered intercurrent events but rather missing data.
- Population-level summary: difference in mean change from baseline to Week 12 in the daily step count averaged over 2-week intervals (i.e., difference is based on subtracting the average of daily step count for Week 11 and Week 12 from the baseline 14-day average daily step count) between two randomized groups.

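### The SAP defines the step-count change as baseline minus Weeks 11-12, so the first key secondary estimate, if programmed as written, carries the wrong sign; the test itself is unaffected

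*SAP*

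**What the plan says.** The first key secondary objective in SAP Section 1.1 is superiority over placebo "to determine the superiority of the effectiveness of canagliflozin 100 mg daily versus placebo in improving the total daily step count". Section 5.3.1 names the endpoint as the "change in the daily step count from baseline to Week 12 averaged over two-week intervals", and the baseline window is Study Days 1 to 14. It then gives the calculation: the change "will be based on subtracting the average of daily step count for Week 11 and Week 12 from the baseline average for each participant".

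Section 5.3.2 uses the same endpoint name, without a formula, for the variable attribute of the estimand. In the population-level summary it adds in parentheses that the "difference is based on subtracting the average of daily step count for Week 11 and Week 12 from the baseline 14-day average daily step count".

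Section 5.3.3 plans two analyses of this endpoint. One is a mixed model that follows the primary endpoint's approach. The other is a two-sided t-test on the difference in mean changes between the groups. Neither description gives a direction of subtraction. SAP Section 1.3 and Protocol Sections 3, 9 and 9.1 speak only of a change, a mean difference or a mean.

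**The concern.** Subtracting A from B gives B minus A, so both formulas yield baseline minus Weeks 11-12. The objective is to raise step count, and Section 5.4.2 grades fewer than 3,000 steps a day as low activity and 6,000 or more as high. More steps is therefore better, and the written rule scores every gain as a loss.

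These sections are operative. Section 5.1.2 says that an outside vendor builds the analysis files to the sponsor's and the SAP's specifications, so a programmer may implement the formula literally. Three things are then at stake:

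- **Direction of the estimate.** A benefit of canagliflozin would appear as a negative difference, and its confidence interval would be reversed too.
- **Agreement between the two planned analyses.** On the primary endpoint a gain is an improvement: higher KCCQ scores are better (SAP Appendix 1), and the responder analysis counts 5- and 10-point improvements (Section 5.2.3). If the mixed model takes that convention and the t-test takes the Section 5.3.1 formula, one endpoint is reported with two opposite signs.
- **Associations.** Sections 5.3.1 and 5.4.2 plan to relate the change in steps to patient-reported measures and clinical outcomes. Those associations would change sign.

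The decision rule would not flag the problem. The hierarchy in Section 1.3 gates on a two-sided p-value, which is the same for a benefit and for a harm of equal size.

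**Working it through.** The plan states no effect size, standard deviation or power for step count, so it has no figure of its own to reproduce. The check concerns the direction of the subtraction. All step counts below are assumptions for illustration; the conclusions about sign hold for any values.

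**1. One participant.** Assume a baseline average B = 4,000 and a Weeks 11-12 average W = 5,000.

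- Rule as written: B - W = 4,000 - 5,000 = -1,000.
- Usual change from baseline: W - B = 5,000 - 4,000 = +1,000.

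**2. Two groups.** Assume that canagliflozin goes from 4,000 to 5,000 and placebo from 4,000 to 4,500, and that the difference is canagliflozin minus placebo.

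- Rule as written: (4,000 - 5,000) - (4,000 - 4,500) = -1,000 - (-500) = -500.
- Usual direction: (5,000 - 4,000) - (4,500 - 4,000) = 1,000 - 500 = +500.

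**3. Effect on the test.** Multiplying every participant's change by -1 turns the estimate D into -D, leaves its standard error as it is, and turns t = D/SE into -t. The two-sided p-value depends only on the absolute value of t, so it does not move. A confidence interval (L, U) becomes (-U, -L). In a linear or mixed model, negating the response negates the fixed effects and leaves the covariance estimates alone, so the same holds there.

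**4. Numerical confirmation.** One simulated data set had 220 participants per group, baseline mean 4,000 and SD 1,500, SD of change 1,500, and a true gain of 500 steps on active treatment. A baseline-adjusted linear model stands in for the mixed model.

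| | Baseline minus Weeks 11-12 (as written) | Weeks 11-12 minus baseline |
|---|---|---|
| Difference in mean change | -694.7 | +694.7 |
| t statistic | -4.62 | +4.62 |
| Two-sided p, t-test | 5.1 × 10⁻⁶ | 5.1 × 10⁻⁶ |
| Baseline-adjusted difference | -694.5 | +694.5 |
| Two-sided p, adjusted | 5.2 × 10⁻⁶ | 5.2 × 10⁻⁶ |

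The standard error is 694.7/4.62 = 150.4 in both columns. The approximate 95% interval for the unadjusted difference is 694.7 ± 1.96 × 150.4, or about 400 to 990, in the usual direction. As written it is about -990 to -400.

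**5. Which associations move.** Section 5.4.2 plans two kinds of analysis. One correlates total steps per day with clinical events. It uses the level of activity and is unaffected. The other relates the change in steps or floors to outcomes and patient-reported measures, as does the comparison foreseen in Section 5.3.1. These reverse.

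**The case against.** The best case for leaving the text alone is that this is an inverted phrase of no inferential consequence. The endpoint name and the estimand's variable attribute both point to the usual meaning, and Section 5.3.3 sends the mixed model to the primary endpoint's convention. A careful programmer would probably compute Weeks 11-12 minus baseline anyway. Section 5.3.3 also presents the 14-day averages themselves, so rising averages beside negative changes would help expose a reversal. All of this stands, and it limits the weight of the point. It does not remove the point: the only explicit formula in the plan is the reversed one, and it sits in both the endpoint definition and the estimand.

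A reader might infer more than the documents support:

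- **That the reversal is deliberate because it appears twice.** The two sentences are nearly identical in wording, which fits one slip copied across equally well.
- **That the comparison with the 1,000-step benchmark is reversed.** Section 5.3.1 gives the benchmark as a change of about that size, without a sign. A comparison of magnitudes is unaffected.
- **That every step-count association flips.** The correlation of daily step level with events does not.
- **That the hierarchy is damaged because its two endpoints run in opposite directions.** They are tested separately and never combined. The SAP already mixes directions, since lower is better on PGIC and PGI-S.
- **That a benefit would be reported as harm.** This needs literal programming and also a failure to notice the sign against the tabulated averages.

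**Conclusion.** The point holds as an error in an operative definition. As written, Sections 5.3.1 and 5.3.2 score an increase in walking as negative, against the endpoint's own name. Taken literally, this fully reverses the sign of the first key secondary estimate, its confidence interval and the associations based on step-count change. It also opens a possible sign conflict between the t-test and the mixed model. The size of the effect, its standard error, the two-sided p-value, power and Type I error control are all unchanged.

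The conclusion assumes that more steps is the beneficial direction, which Sections 1.1 and 5.4.2 support. The statement that a benefit appears as a negative difference further assumes canagliflozin minus placebo. The possible conflict between the two analyses assumes that the mixed model takes post-baseline minus baseline, as the primary endpoint's improvement convention implies. The point should be corrected, but it does not threaten the validity of the test.

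**What to change.** In SAP Sections 5.3.1 and 5.3.2, replace the formula with: subtracting the baseline average from the average for Week 11 and Week 12; positive values indicate improvement. State in Section 5.3.3 that the mixed model and the t-test both use this direction. Apply it also to the changes from the 3-, 5- and 7-day averages and to floors climbed, for which Section 5.3.1 gives no sign.

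The cost is a few sentences in the SAP and a matching line in the programming specification. Design, sample size, data collection and the testing hierarchy do not change.
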